We propose a pilot and feasibility trial to use continuous glucose monitoring (CGM) in youth with type 2 diabetes (T2D) and public insurance. This feasibility trial would fill a gap in the literature with respect to CGM use in youth with type 2 diabetes. The findings from this trial can provide much needed data to pave the way for future studies using CGM technology in this population. Our proposal is focused on youth with public insurance, seeking to provide diabetes technology for patients and their families to use in daily diabetes management. This pilot is an expansion of our existing program of CGM access to youth with type 1 diabetes which has led to an improvement HbA1C of 0.5% over 1 year and positive feedback from patients and families.^{1,2}

Specific Aim 1: Evaluate the feasibility of CGM start and continuation in youth with T2D and describe glucose metrics and patient reported outcomes (PROs). We will pilot and refine a program to test the hypothesis that CGM start and continuation in youth with T2D is feasible and then evaluate glucose metrics and PROs.

Hypothesis 1a: In phase 1, CGM use exceeding >50% of participants will be feasible and sustainable in youth with T2D, measured by days of CGM use per 2-week period (>75%). **H1b:** Following an additional needs assessment after phase 1, in phase 2 sustained CGM use per 2-week period (>75%) will exceed 75% of participants. **H1c:** Based on completion of PROs surveys, it is expected that diabetes-specific distress will decline, and overall well-being/quality of life will improve. Secondary outcome PROs (see protocol synopsis) collected at baseline will be associated with HbA1c and diabetes management outcomes. Data on glucose metrics, SDOH, and needs and barriers will be described.

Specific Aim 2: To assess the clinical outcomes (HbA1C, time in range [70-180 mg/dL], time in hypoglycemia [<70 mg/dL]) of individuals participating in this trial compared to clinic historical controls.

Hypothesis 2: Use of CGM will improve HbA1C and other clinical metrics of diabetes glucose control.

Measured Outcomes:

1. Sustained use of CGM by patients over one year measured by days of CGM use per every 2-week period with >80% as goal.
2. Change in HbA1C over first year of CGM use
3. Glucose profile metrics: percentage time in range, time in hypoglycemia, and time in hyperglycemia obtained from CGM.
4. Change in weight and BMI over first year of CGM use using clinic visit weight and BMI measurements.
5. PROs

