Unmeasured, but documented metrics:

Reported challenges with CGM use as documented by clinical team (MD/NP, CDE)

Tracking of patients who are able to obtain insurance coverage for CGM at completion of study

Background and Significance

T2D is **increasingly affecting children of minority and lower SES backgrounds, with higher rates of diabetes complications, specifically cardiovascular and renal co-morbidities in youth with T2D compared to youth with T1D** and similar duration of disease ³⁻⁶. Two national multi-center studies, the RISE Consortium and the Treatment Options for Type 2 Diabetes in Adolescents and Youth (TODAY) Study reported more rapid beta-cell damage, disease progression, and diabetes-related complications in youth compared to adults, highlighting the need for improved clinical management and treatment for these patients⁶⁻⁸. By one year after diagnosis, a majority of youth with T2D are not meeting HbA1c targets recommended by the ADA and the International Society of Pediatric and Adolescent Diabetes (ISPAD)⁹⁻¹¹

Treatment of T2D includes lifestyle and diet management along with medications often including multiple daily injections of insulin, frequently in a complex psychosocial and cultural environment that challenge durable adherence to medical care. CGM is available for youth with T1D as an alternate to self-monitoring blood glucoses (SMBG) and data in adults with T2D demonstrates efficacy and cost effectiveness¹²⁻¹⁴. Youth with T2D have similar SMBG and insulin requirements, but have little to no access to CGM due to a lack of insurance coverage, usually public insurance, for CGM in this patient population.

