- The care team member initiating the CGM will ask patients and their caregivers if they are interested in hearing about this study to understand the use of CGM in youth with type 2 diabetes
- If a patient and/or caregiver is interested in this study, one of the study team members will discuss the study with the participant and obtain informed consent and assent (if needed).
- Participants who consent to be part of this study will have the appropriate CGM applications and readers active (Libre 2 CGM, LibreView, LibreLink) as per standard clinical care.

1. Informed consent and assent - this can be done in person or virtually
2. CGM start – done by CDE in clinic
 - a. 4 weeks of supplies given – CRC to confirm with family preferred way to get supplies every 6 weeks and best way to contact them.
 - b. Standard clinic CGM education
3. Routine clinic visit

4. PRO completion - participants who speak and write English and Spanish will be asked to complete PROs surveys

Visits 2a,3a,4a,5a:

1. CRC check in with family/patient
 - a. Confirm CGM use
 - b. Address CGM issues – CRC to address or forward to CDE if clinical question
 - c. Ship or arrange for supply pick up (6 weeks of supplies)
 - d. Confirm next clinic visit

Visits 2,3,4,5,6:

[figure not shown]
1. Routine Clinic visit including CDE visit. The purpose of these visits is to reinforce prior teaching, answer questions, and review CGM data, making changes as necessary to the patient's care regimen to better control their diabetes.
2. CRC check in, supplies provided (for all visits except visit 6)
3. PRO questionnaires administered for visits 3 and 6

Biostatistical plan

Statistical methods: We will generate descriptive statistics for all participants included in the study and will create a STROBE diagram²⁶ to describe participants screened, recruited, and followed in both study phases. To address the feasibility of CGM use in T2D, we will estimate the proportion of participants who have sustained CGM use in both phase 1 and 2. Our feasibility analysis will include all participants. To address H1c, we will fit linear regression models using GEE to estimate the association of PROs with longitudinal HbA1c. Logistic regression models fit with GEE will be used to estimate the association of PROs with dichotomous diabetes management outcomes (e.g., presence of diabetes distress).

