At each visit we will collect descriptive data on CGM use, clinical glucose outcome metrics, and provide CGM supplies. Mixed affects modeling will be used to characterize the trajectory of measured variables and to account for patient-level correlation of this data. To account for gaps in CGM use we will use intention to treat analysis and consider a censoring method for a patient who leaves the practice or are lost to follow up. We will also perform an exploratory analysis of the relationship at a patient-level between days of CGM wear and time in range.

Study Timeline

Data Collection and Entry

1. Study participant data entry will be collected and entered in Stanford RedCap by the study team.
2. PRO will be collected in RedCap

The initial survey is filled out in person during the CGM visit during which, parents provide an email that will be the platform for contact for the future surveys. At the follow up points, the RedCap data base will automatically trigger survey link to the email on file. If the survey is not completed, a second email is sent as a reminder followed by provider team reminders. Participant data will be included for analysis for the time frames that are available when.

These measures will assess issues of adherence or illness distress and provide valuable information for providers to better understand the impact of early CGM initiation. The patient/guardian will have the option of filling out the questionnaires in English or Spanish. Based on the evidence in the PROs literature and our clinical experiences, we have developed an algorithm for responding to PROs screen scores that are outside of the normative range triggers a response from social worker and/or diabetes psychologist²⁷. Study personnel will complete a chart review to collect relevant health information including diagnosis, duration of disease, indicators of health status, and regimen information (e.g. medication, doses). These medical record data are required to assess the validity and usefulness of the clinical PROs screening measures. Additionally, reliability analysis will be conducted to examine the psychometric properties of the PROs measures, and the satisfaction questionnaire data will be aggregated to assess the acceptability of the PROs procedure from the patient's perspective.

- PROMIS global health (youth): BELOW 22 for the PROMIS global health scale. Anyone who scores 21 or lower would trigger an alert to place a diabetes psychology referral.

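### The models assigned to H1c estimate only its association half and lack two safeguards (small-sample variance, no circular predictor); the change half is left to a mixed model not tied to it

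*Combined protocol and SAP*

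**What the plan says.** Under Specific Aim 1, H1c makes two statements. The first is directional: "it is expected that diabetes-specific distress will decline, and overall well-being/quality of life will improve". The second concerns secondary PROs, which "collected at baseline will be associated with HbA1c and diabetes management outcomes". The aim itself is worded more modestly, to "describe glucose metrics and patient reported outcomes (PROs".

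The Statistical methods paragraph assigns two models to this hypothesis. The first: "To address H1c, we will fit linear regression models using GEE to estimate the association of PROs with longitudinal HbA1c". The second is a logistic GEE for the "association of PROs with dichotomous diabetes management outcomes (e.g., presence of diabetes distress". Neither sentence names a variance estimator, a time effect or a comparison with baseline.

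The next paragraph of the plan adds: "Mixed affects modeling will be used to characterize the trajectory of measured variables and to account for patient-level correlation of this data". It mentions no hypothesis, score, respondent or visit contrast. PROs are item 5 of the Measured Outcomes list, which stands against a separate list headed "Unmeasured, but documented metrics", so they fall naturally among the measured variables.

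PROs are collected at visit 1, and the visit list adds "PRO questionnaires administered for visits 3 and 6". The PRO survey table gives three distress scores (youth, parent proxy, parent's own distress) and three quality-of-life or well-being scores (PedsQL youth, PedsQL parent proxy, PROMIS Global Health). Phase 1 has 30 participants and phase 2 has 50.

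**The concern.** A reader who looks up how H1c will be analysed finds models for only one half of it. Whether distress fell or quality of life rose has to be answered by a model that the plan does not connect with the hypothesis, using a score, respondent and visit chosen later.

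The association half has two technical weaknesses. The ordinary GEE sandwich variance is justified for a large number of clusters, and here the clusters are 30 to 80 participants; intervals that are too narrow would make baseline PROs look more predictive of HbA1c than the data support. Also, presence of distress is offered as an outcome in a model whose predictors are PROs, and distress is itself a PRO. A regression of distress on the distress score would give a strong association that says nothing about diabetes management.

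The Community Partnership section says that results will go to public-insurance leadership in support of CGM coverage, so a PRO finding may be read outside the research setting.

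**Working it through.** The plan gives no significance level, SD, correlation or sample-size calculation for H1c, so there is no figure to reproduce. The inputs below that are not in the documents are assumptions.

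**1. Hypothesis against model.**

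| Part of H1c | Model introduced for H1c | Other model that could serve |
|---|---|---|
| Distress down, quality of life up | None: neither GEE model states a time effect or baseline contrast | Mixed model of trajectories, not linked to H1c |
| Baseline PROs associated with HbA1c | Linear GEE | – |
| Baseline PROs associated with management outcomes | Logistic GEE | – |

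**2. Size of the GEE problem.** Numbers of participants: 30 (phase 1), 50 (phase 2), 30 + 50 = 80 (pooled). Take balanced visits, an exchangeable working correlation and a baseline predictor x. The linear GEE slope then equals the least-squares slope of participant-mean HbA1c on x, whatever the within-participant correlation. With residuals e and D = Σ(x − x̄)²:

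- uncorrected sandwich (HC0): variance = Σ(x − x̄)²e² / D², referred to z;
- Mancl-DeRouen (here equal to HC3): e is replaced by e/(1 − h), where h = 1/n + (x − x̄)²/D, referred to t with n − 2 degrees of freedom.

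The true slope was set to zero, with 40,000 replicates and nominal two-sided 5%. The skewed PRO is lognormal with sigma 0.8.

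| | n=30 | n=50 | n=80 |
|---|---|---|---|
| Uncorrected, normal PRO | about 9% | about 7.5% | about 6.7% |
| Uncorrected, skewed PRO | about 14% | about 12% | about 10% |
| Corrected, normal PRO | 5.0–5.3% | 5.0–5.3% | 5.0–5.3% |
| Corrected, skewed PRO | 5.6–6.5% | 5.6–6.5% | 5.6–6.5% |

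Repeat runs with other seeds agree to within about half a percentage point. The logistic GEE was not simulated.

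**3. Circularity.** Suppose later distress is the top 20–40% of a score whose retest correlation with baseline is 0.4, 0.55 or 0.7. The odds ratio per SD of the baseline distress score is then 2.1–2.2, 3.0–3.2 or 5.3–5.7, from retest correlation alone. If score and outcome came from the same visit and the outcome were a cut of that score, the predictor would determine the outcome.

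**4. Open choice in the change half (illustration only).** Candidate scores: 3 + 3 = 6. Contrasts with visit 1: visit 3 and visit 6. Candidate comparisons: 6 × 2 = 12. Assume normal scores, between-visit correlation 0.55, between-score correlation 0.3–0.7, n = 21, 30 or 50, paired t-tests at two-sided 5%, and no true change.

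| Favourable, nominally significant result on | Chance |
|---|---|
| Any of the 6 scores, either contrast | 14–21% |
| At least one distress and at least one quality-of-life score | 3–5% |
| Either of two pre-named scores, one contrast | 4–5% |
| Both of two pre-named scores, one contrast | 0.2–0.8% |

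**The case against.** The strongest reply is that this is a missing cross-reference in a pilot. The mixed model can cover PRO change, the visits, instruments and respondents are listed, and Aim 1 promises description. H1c also refers to a protocol synopsis that is not in the documents and may name the PRO scores. All of this stands, and it is why the point is minor.

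Four stronger readings are tempting, and the documents do not support them.

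- *No analysis of change is planned.* The mixed model of measured variables, read with the Measured Outcomes list, can reasonably include PROs. The sentence just before it names only CGM use and glucose metrics, so that reading is generous, but it is available.
- *H1c carries a 14–21% false-positive risk.* The plan states no alpha and no test for it. H1c also requires distress to fall and quality of life to rise, for which the figure is 3–5%. If any one result is to count, the fair comparator for two named scores is 4–5%, not the 2.5% of a single contrast.
- *The planned GEE has a 9–14% error rate.* The plan names no estimator. The figures apply only if the uncorrected sandwich with a normal reference is used, although that is the usual form.
- *A circular model has been proposed.* PROs also include PedsQL, PROMIS and technology comfort. The plan does not say that the distress score will predict distress, but it does not exclude it either.

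**Conclusion.** The point holds as a minor one. The models introduced for H1c estimate associations only, and its directional half depends on a mixed model that is not tied to it. In the association half, two changes improve on the plan as written. A small-sample correction brings type I error from about 9%, 7.5% and 6.7% (n = 30, 50, 80; normal PRO), or about 14%, 12% and 10% (strongly skewed PRO), to about 5–6.5%. Excluding the distress score when distress is the outcome removes a possible circularity.

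The error rates assume balanced visits, a baseline predictor, a linear model and the uncorrected sandwich as the default. Age limits on the youth forms and missed surveys would reduce the numbers and make the problem somewhat larger: with 70% of 30 participants on a form (0.7 × 30 = 21), the uncorrected rate is 11.2% for a normal PRO. What the absent synopsis says about scores cannot be judged. The feasibility endpoint is unaffected.

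**What to change.** 1. Fit the GEE models with a small-sample corrected variance, for example Mancl-DeRouen, and a t reference. The cost is wider intervals. At n = 30, 50 and 80 the typical increase is about 18%, 10% and 6% for a normal PRO. For a strongly skewed PRO the median increase is about 27%, 18% and 13%, and the mean increase 41%, 27% and 19%.
2. Where presence of distress is the outcome, leave the distress score out of the predictors. This costs nothing.
3. State that the change half of H1c is answered by the mixed model, with visit (1, 3, 6) as a factor and small-sample degrees of freedom. The latter matter here too: a z reference on the complete-pair contrast gives 6.4% type I error at 21 participants and 7.0% at 15. Report the final-minus-baseline difference with a 95% confidence interval for one named distress score and one named quality-of-life score, each with its respondent. Describe the remaining scores. Present the result as a single-arm before-after change, not as an effect of CGM.

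If the synopsis already names the scores, a cross-reference to it is enough for that part. The changes are a few sentences in the Biostatistical plan and need no new data on the 12-month schedule. Scores that are not named become descriptive only.

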Significant improvements in HbA1C have been shown in youth with type 1 diabetes with public insurance with uninterrupted CGM use.²² This real-world data in youth with type 1 diabetes has complimented research study data and paved the way for earlier and easier CGM approval for youth, particularly publicly insured youth.

Our team has shown that youth with T1D with public insurance who have uninterrupted CGM use compared to those who lose CGM coverage due to insurance issues have significant improvements in HbA1c^{22,23}. This real-world data in youth with T1D has complimented research study data and paved the way for earlier and easier CGM approval for youth, particularly publicly insured youth. We aim to translate these learnings to our T2D population. In our clinic, youth with T2D have a mean HbA1c of 8.6% with only 35% at goal HbA1c of <7% (n=311 HbA1c values), indicating that the majority of youth with T2D are not meeting this significant diabetes therapy goal. Reflective of the national data demonstrating youth with T2D are overwhelmingly minorities and from families of lower SES, a significant portion of our T2D patient population (n=131) is publicly insured (77%), minority status (73% and Latinx 66%), and has Spanish-speaking parents or guardians (56%), all groups which have lower rates of diabetes technology use^{11,24}.

Design: This will be a two-phase pilot program focused on youth with T2D to evaluate initiation and sustained use of CGM. The focus of phase 1 will be a feasibility trial to use CGM in 30 youth with T2D and public insurance over a 12-month period. CGM will be provided to all participants. Education for youth and their families about CGM integration in diabetes care will be provided throughout the study. Barriers to CGM adoptions and sustained CGM use will be tracked throughout this phase to inform the further refinement of the program in phase 2 in 50 youth with T2D. As part of closing the disparities in diabetes technology use in youth with T2D, QoL and PROs will be evaluated. The goals of phase 2 are to utilize human factors design data, QoL and PRO metrics collected in phase 1 to address identified needs and barriers to increase initiation and continued use of CGM in this population.

Inclusion criteria

1. Diagnosis of T2D (diabetes autoantibody negative) followed in the Pediatric Endocrinology clinic at Stanford Children's Health

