2. HbA1C greater than 6.5% at enrollment. This is to enroll patients who are working on improving glucose control but are still not meeting HbA1c targets.^{9,25}
3. Interested in starting on a continuous glucose monitor
4. Access to a mobile device that is compatible with CGM applications or willing to use CGM receiver which will be provided. Both the receiver and mobile device allows patients to view glucose data and alerts from the CGM and upload glucose data during or in between in-person or virtual clinic visits, not necessitating that the participant have access to a mobile device.
5. Public insurance
6. Age 4-20 years inclusive

Exclusion criteria

1. Non-T2D diagnosis
2. HgA1C < 6.5%
3. Participant not willing to wear CGM
4. Private insurance

Procedures and Methods

Recruitment: The study team will review clinic schedules to identify youth with T2D from the patients in our clinic who would qualify. The informed consent process will be conducted prior to initiating the study. Following CGM initiation by a CDE, youth will have a routine 1-week clinic follow up with our diabetes team and then will be seen per clinic standard of care, every 3 months thereafter for the 12 months of the study duration. At each visit we will collect descriptive data on CGM use, CGM glucose metrics, and provide CGM supplies. PROs will be evaluated at three time points during the study. In phase 2, we will identify a new cohort of eligible patients who will be evaluated at a similar cadence as phase 1.

Visit	1	2	2a	3	3a	4	4a	5	5a	6
Weeks from start	x	2 weeks	4-6 weeks	12 weeks						
Informed consent and assent Visit Type ** this will be modified if LibreView App is available during study duration, can move visits to TH with lab A1C	x (can be done in person or via TH)									
	In person	IP/TH	phone/IP	IP	phone/IP	IP	phone/IP	IP	phone/IP	IP
Demographics	x									
Diabetes History	x									
HbA1C	x			x		x		x		x
CGM start	x				x					x
PROs	x			x						x
CGM metrics	x	x	x	x		x		x		x
CGM education	x	x	x			x		x		x
CRC check on supplies (confirm use and shipment)	x	x	x	x	x	x	x	x	x	x
Final study visit										x

Visit 1:

- Participants will be offered the opportunity to start on CGM at their scheduled clinic visit
- Participants will receive CGM education from a certified diabetes educator (CDE)

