Participants may have challenges with CGM supplies, upload of glucose data, or questions about CGM use. Our team will be available to patients and their families to address these issues including attempts to avoid gaps in CGM supplies to support continuous use of CGM. If a patient misses more than 3 appointments or decides to stop using CGM they will be withdrawn from the study and asked to resume usual care. We are in the process of obtaining CGM supplies for all participants for the duration of the study to ensure continued access to CGM supplies. If we are not able to secure funding for CGM supplies we will use budgeted funds from this grant to cover the cost of CGM supplies for 50 participants over 6 months in place of salary support for a research assistant and home HbA1C kits, with the PI salary support going towards PI FTE towards completing study related tasks and working with participants to facilitate an in-person clinic visit. Even with a shorter duration, the study can provide meaningful pilot data about the feasibility of CGM use and key clinical outcomes in youth with T2D.

Future Steps

Data from this feasibility trial would fill a gap in the literature with respect to CGM use in youth with type 2 diabetes. The findings from this trial can provide much needed data to impact CGM coverage policy for publicly insured youth with type 2 diabetes in California and pave the way for future studies using CGM technology in this population.

References

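### The H1c GEE models carry no small-sample correction for cohorts of 30 and 50, so default 95% intervals would cover only about 88–93%

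*Combined protocol and SAP*

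**What the plan says.** For the association part of H1c, the Biostatistical plan says "To address H1c, we will fit linear regression models using GEE to estimate the association of PROs with longitudinal HbA1c". For binary outcomes it says "Logistic regression models fit with GEE will be used to estimate the association of PROs with dichotomous diabetes management outcomes". Neither sentence gives a working correlation, a variance estimator, a small-sample adjustment or a missing-data assumption. H1c in Specific Aims takes the PROs at baseline as the explanatory variables.

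The number of clusters comes from the Design paragraph: "The focus of phase 1 will be a feasibility trial to use CGM in 30 youth with T2D", followed by "further refinement of the program in phase 2 in 50 youth with T2D". The Recruitment paragraph makes the phases separate people: "In phase 2, we will identify a new cohort of eligible patients who will be evaluated at a similar cadence as phase 1". Whether H1c is fitted by phase or on all 80 is not said.

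On incomplete follow-up, Potential Pitfalls and Contingency Plans says "If a patient misses more than 3 appointments or decides to stop using CGM they will be withdrawn from the study". The Biostatistical plan refers to intention to treat and to a censoring method that will be considered. It also says "Mixed affects modeling will be used to characterize the trajectory of measured variables", a separate use of mixed models.

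**The concern.** GEE inference usually rests on the robust (sandwich) variance, which is justified for a large number of clusters. With a few dozen, it is biased downward, because fitted residuals are smaller than true errors, most of all for participants with extreme PRO scores. The z limits add to the problem because they ignore the sampling error of the variance itself. Intervals are then too narrow, and an association between distress and HbA1c looks better established than it is. The protocol intends its results to inform insurance coverage and later studies, so the error bars matter even in a pilot.

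The second issue is withdrawal. Participants who stop CGM leave the study. If they tend to be those with higher HbA1c, GEE that treats visits as independent gives too little weight to what is known about them, and the slope can shrink towards zero. Whether that happens depends on a working correlation that the plan leaves open.

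**Working it through.** The plan gives no alpha, power, SD, effect size or dropout rate for H1c, so there is no planned figure to reproduce.

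**Step 1. Complete data, by formula.** With a baseline PRO score, common visit times and no missing visits, the GEE slope (independence or exchangeable) equals the ordinary regression slope of each person's mean HbA1c on the score. With equal error variance across persons, the expected sandwich variance is the true variance times

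1 − 1/n − Σw², where w = (x − x̄)² / Σ(x − x̄)².

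For roughly normal scores Σw² ≈ 3/n, so the factor is about 1 − 4/n:

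- n=30: 1 − 4/30 = 0.867; SE factor √0.867 = 0.931
- n=50: 1 − 4/50 = 0.920; SE factor 0.959
- n=80: 1 − 4/80 = 0.950; SE factor 0.975

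Were the SE fixed at that fraction, coverage would be 2Φ(1.96 × factor) − 1 = 93.2%, 94.0% and 94.4%. Sampling variation in the SE lowers it further. No HbA1c SD, correlation or slope enters this step; skewed scores raise Σw² and make matters worse.

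**Step 2. Simulation.** From the documents: n = 30, 50 and 80; HbA1c at 5 visits (visit table); clinic mean HbA1c 8.6% (Preliminary Studies). Assumed: HbA1c SD 1.9, within-person correlation 0.7 (AR(1) 0.8 as a variant), slope 0.5 HbA1c points per SD of PRO, normal or right-skewed PRO, and either no dropout or about 30–32% dropout that is completely random, dependent on the last observed HbA1c, or dependent on the current unobserved HbA1c. The model was HbA1c on baseline PRO and time, with 1,500–2,000 replicates per scenario (Monte Carlo error about √(0.915 × 0.085 / 2000) = 0.6 points).

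Coverage of nominal 95% intervals (%):

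| n | Sandwich, z: normal PRO, no dropout | Sandwich, z: normal PRO, 0–32% dropout | Sandwich, z: skewed PRO | Mancl-DeRouen, t(n−3): all scenarios |
|---|---|---|---|---|
| 30 | 91.5 | 87.8–91.5 | 87.5–90.1 | 93.3–95.8 |
| 50 | 92.0 | 90.9–92.9 | 90.1–90.7 | 92.8–95.5 |
| 80 | 92.1 | 91.5–94.2 | 90.4–91.6 | 93.5–95.4 |

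At n=30 the mean SE was about 7–18% too small. Runs with other assumed variances (between-person SD 1.5, slope SD 0.8 per year, residual SD 0.6) and a PRO-by-time slope gave 91.6%, 91.6% and 93.3% without dropout.

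**Step 3. Bias in the slope of 0.5.**

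- Dropout on last observed HbA1c, about 32%, independence correlation: −0.035 to −0.062, that is 0.035/0.5 = 7% to 0.062/0.5 = 12%. Another set of runs gave 12–14%. At about 50% dropout: −0.051 to −0.084 (10–17%).
- Same mechanism, exchangeable correlation: −0.017 to +0.006. REML random-intercept model: −0.001 to +0.009.
- Completely random dropout: 0.010 or less in absolute value for either correlation.
- Dropout on current unobserved HbA1c, same data sets: exchangeable GEE −0.032 to −0.043, mixed model −0.031 to −0.041, about 6–9% for both.

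**Step 4. Scale.** Residual variance is 1.9² − 0.5² = 3.36. The variance of a five-visit mean is 3.36 × (1 + 4 × 0.7)/5 = 2.55, so the slope's SD at n=30 is about √(2.55/30) = 0.29 (about 0.30 simulated). The largest bias at about 32% dropout, 0.062, is roughly a fifth of that.

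**Step 5. Mixed model.** The REML random-intercept model with z limits covered 93.3–94.3% (n=30), 93.8–94.0% (n=50) and 95.5–96.0% (n=80), on only 400 replicates. Kenward-Roger limits and the logistic models were not simulated.

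**The case against.** The best defence is that the plan prescribes none of the harmful choices. It does not say independence, uncorrected or z, and an analyst could choose well. It states no test or alpha for H1c, and the study's focus is feasibility. Pooling would give 80 clusters and a milder shortfall. All of this limits the weight of the point. It does not remove it, because the intervals will be reported and the plan gives no reason to expect a correction.

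Four stronger readings are tempting and not supported:

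- *That GEE biases the association.* A link between withdrawal and HbA1c is an inference: the stated triggers are missed appointments and stopping CGM. If appointments means clinic visits 2 to 6, someone who has missed four of the five has at most one other, so that trigger removes little HbA1c data. Stopping CGM can remove more. Even then, bias from dropout on observed HbA1c was material only with an independence correlation.
- *That attenuation is severe.* A PRO-by-time model can be set up in which a true 0.40 is estimated as 0.24. The plan names no such interaction, and a rerun under the same variances gave 0.37–0.38.
- *That the plan holds two conflicting missing-data assumptions.* The mixed models describe trajectories, GEE estimates a population-average association, and no assumption is stated for either. The sentence "Participant data will be included for analysis for the time frames that are available when" sits among the survey-reminder procedures and says little about HbA1c visits.
- *That mixed models must replace GEE.* Corrected GEE performs well here, and a logistic mixed model would change what the binary coefficients mean.

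**Conclusion.** The point holds for interval width. With 30 or 50 participants, the standard sandwich with z limits gives nominal 95% intervals that cover about 88–93%, and about 92–94% at n=80 with roughly normal scores (90–92% with skewed ones). The lower values belong to scenarios with dropout or skewed scores. The complete-data shortfall needs no dropout assumption and follows mainly from the number of participants and the shape of the PRO distribution.

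The bias is conditional: roughly 7–14% attenuation at about 30% dropout, only if withdrawal depends on observed HbA1c and the working correlation is independence. It is small beside the sampling error of the slope. Its size rests on assumed SD, correlation, slope and dropout values.

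The change is worth making, but nothing here affects the CGM-use proportions that answer the feasibility question.

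**What to change.** For the HbA1c models, write one of these into the Biostatistical plan:

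1. GEE with an exchangeable working correlation, Mancl-DeRouen variance and t limits; or
2. a REML linear mixed model with Kenward-Roger or Satterthwaite degrees of freedom.

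Under either, include every HbA1c value up to withdrawal, and say whether the phases are analysed separately or pooled. For the dichotomous outcomes, keep the marginal logistic GEE with the same small-sample correction; its performance was not simulated here. State that either option for HbA1c relies on dropout depending only on observed data, since neither protects against dropout driven by unobserved HbA1c.

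The cost is a few sentences, a different option or procedure in the software, and slightly wider intervals. At n=30 the t(27) limit alone is 2.05 against 1.96, about 5% wider before the variance correction. No new data are needed.
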